#### The Intent-to-Treat (ITT) Set

The Intent-to-Treat (ITT) Set is defined as all participants who are randomized and receive at least one dose of nusinersen; participants will be analyzed in the treatment group to which they are randomized. This will be the primary population for the analysis of efficacy endpoints.

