The p-value associated with the observed test statistic is then calculated using a reference distribution generated by the re-randomization procedure described below:

- 1. For all 75 subjects randomized in the ITT population, randomly assign subjects in a 50/25 ratio to treatment (nusinersen 58/28 mg or control) such that there are 50 subjects in the nusinersen 58/28 mg group and 25 in the control group. This can be done using simple random sampling without replacement. The seed used will be 5846894.
- 2. Calculate the trimmed-mean test statistic as described above using the random treatment assignment in Step 1
- 3. Repeat Steps 1 and 2 N times (N=10,000). As a result, N trimmed-mean statistics will be generated. The empirical distribution of the N trimmed-mean statistics will then serve as the reference distribution for p-value calculations.

Denote the observed trimmed mean statistic as T0. Once the reference distribution has been established, the p-value associated with the observed test statistic is calculated as proportion of simulated test statistics that are either greater than |T0| or less than - |T0|.

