### Supplementary Analyses

In order to provide additional understanding of the treatment effect, two supplementary analyses will be performed on the primary endpoint. The first, in order to provide an estimate of the difference in CHOP INTEND using an ANCOVA model at each timepoint the MI dataset generated for the primary endpoint will be utilized. As a sensitivity analysis, this will be repeated using an ANCOVA model where the variance in each treatment group is estimated separately.

The second will utilize the following estimand which is described as the trimmed mean:

- Population: The ITT Set is considered and the treatment arm with the highest % of participants withdrawn by Day 183 is determined (labelled X). The same fraction is applied to the other treatment arm and the analysis is performed on (100-X) % of the ITT Set
- Variable: difference between treatments in the endpoint means in the (100-X) % subset of participants with the most favorable outcomes,
- Handling of intercurrent events: Due to the population definition, the intercurrent events of death or withdrawal from study are dynamically trimmed from the ITT Set. The assumption here is that any ICE is an equally bad outcome.
- Population level summary ANCOVA

These analyses are further described in Section in Section 6.1.

Product: Nusinersen
Study: 232SM203

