## Table 4: CHOP INTEND: Change from baseline to Day 183, accounting for mortality/dropout. Comparing the 50/28-mg Group to Study CS3B Sham Control

Туре	Analysis Method	Analysis Population: Further Notes	
Primary Analysis	Joint rank using multiple imputation (MI)	Matched Sham Set	
Sensitivity Analysis	Joint rank using multiple imputation (MI)	Matched Sham Set (sensitivity)	
	Joint rank using multiple imputation (MI)	Greedy matched set (sensitivity)	
	Adjustment of ranking criteria for JRT for withdrawals not due to death	Matched Sham Set	
	Adjustment of ranking criteria for JRT for permanent ventilation	Matched Sham Set	
	Subjects who died will be excluded from the MI model	Matched Sham Set	
	Joint rank using multiple imputation (MI)	Matched Sham Set. Data truncated to only include data up to Day 183 (inclusive).	
	Joint rank using Jump to Control MI	Matched Sham Set	
	Rank based implementation of joint rank method + MI	Matched Sham Set	
	Joint rank test using multiple imputation (MI), ANCOVA model not assuming equality of variance	Matched Sham Set	
	Joint rank using multiple imputation (MI) by disease duration	Matched Sham Set	
	Joint rank using multiple imputation (MI) by baseline CHOP INTEND	Matched Sham Set	
Supplementary Analysis	Trimmed mean	Matched Sham Set	

Product: Nusinersen

Study: 232SM203

Page 40

Endpoint and Comparison	Analysis Method	Analysis Population: further notes
Supplemental analysis		
Difference (50/28mg- Matched Sham Control) in change in CHOP INTEND from baseline by visit	ANCOVA using MI	Matched Sham Set
Difference (50/28mg- Matched Sham Control) in change in CHOP INTEND from baseline by visit	ANCOVA using MI (Not assuming equality of variances)	Matched Sham Set

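### The trimmed-mean p-value is built by permuting the 75 trial participants, but the analysis is planned only for 50/28 mg versus CS3B sham, so the reference distribution belongs to another comparison

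*SAP*

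**What the plan says.** All references are to the Part B infantile-onset SAP, version 3.0.

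- **Section 6.1, Trimmed mean.** The method is illustrated with a case labelled hypothetical, 12 mg versus 50/28 mg within the trial. The p-value procedure follows. Step 1 reads "For all 75 subjects randomized in the ITT population, randomly assign subjects in a 50/25 ratio to treatment". A seed is fixed, the steps are repeated 10,000 times, and "the p-value associated with the observed test statistic is calculated as proportion of simulated test statistics that are either greater than" the absolute value of T0 or less than its negative. The higher-dose arm is twice called 58/28 mg here.
- **Section 6.3.1, Supplementary Analyses.** The trimmed-mean estimand states: "Population: The ITT Set is considered and the treatment arm with the highest % of participants withdrawn by Day 183 is determined".
- **Section 3.6.1.** The ITT Set is "all participants who are randomized and receive at least one dose of nusinersen".
- **Table 4.** Its title ends "Comparing the 50/28-mg Group to Study CS3B Sham Control", and its supplementary row reads "Trimmed mean Matched Sham Set".
- **Table 1 and Section 6.2.** The Matched Sham Set holds all higher-dose ITT participants and a subset of the 37 CS3B sham subjects. The matching aims for as many as are comparable and stops at 20.
- **Tables 9 and 10** (50/28 mg versus 12 mg) list ANCOVA as the supplementary analysis and no trimmed mean.

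**The concern.** A permutation test is valid when the labels being shuffled belong to the subjects being compared. Here the observed statistic is 50/28 mg minus sham. The written reference distribution leaves out every sham subject and includes 25 infants on 12 mg who are not in the comparison. Its spread reflects the 12 mg arm's size and outcomes, not those of the sham group. The resulting p-value would be reported in support of the primary endpoint although its error rate for that comparison is not controlled.

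A smaller point concerns the p-value rule. It is the raw proportion of draws strictly beyond the observed value, so it can equal exactly 0. A Monte Carlo permutation p-value that counts the observed arrangement cannot.

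**Working it through.** **Inputs from the SAP.** Section 2.3: 50 higher-dose and 20 sham; difference 24 points versus sham, SD 8.8, survival benefit 23 percentage points; 4.5 points and 3 percentage points over 12 mg; two-sided 5%. Section 6.2: 20 to 37 sham. Section 6.1: 75 participants split 50/25.

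**Derived.** 12 mg minus sham = 24 − 4.5 = 19.5 points, with survival benefit 23 − 3 = 20 percentage points.

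**Assumed.** Sham survival at Day 183 is not given; 60%, 70% and 75% were tried.

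**1. The plan's own figures.** SE = 8.8 × sqrt(1/50 + 1/20) = 2.33 and 24/2.33 = 10.3, so normal-approximation power is 1.000. This agrees with the stated power of at least about 99%, which came from joint-rank simulation. The hypothetical example also checks: 4/50 = 8%, 5/25 = 20%, so 80% is retained. The SAP gives no figure for the reference distribution itself.

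**2. No true difference, no trimming.** With a common SD, the permutation SD is proportional to sqrt(1/n1 + 1/n0):

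- as written, 50/25: 0.245
- Matched Sham Set, 50/20: 0.265
- Matched Sham Set, 50/37: 0.217

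The written version is too narrow below 25 sham, equal at 25 and too wide above.

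**3. No true difference, trimming as in Section 6.1.** All groups equal, survival 75% or 90%, 1,500 simulated trials with 500 permutations each:

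| Sham subjects | Reference SD, written versus Matched Sham Set | Rejection at nominal 5%, written | Rejection, Matched Sham Set |
|---|---|---|---|
| 20 | about 8% smaller | 7.6% to 8.5% | 5.1% to 5.2% |
| 30 | about 4% larger | 5.2% to 6.1% | 5.6% to 6.3% |
| 37 | 9% to 10% larger | 3.1% to 3.5% | 4.6% to 5.1% |

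Monte Carlo standard error near 5% is sqrt(0.05 × 0.95/1,500) = 0.6 percentage points.

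**4. Dependence on the 12 mg arm.** Suppose higher dose equals sham while 12 mg is 19.5 points better. Without trimming, the written SD is sqrt(8.8² + 19.5² × (50 × 25)/75²) × 0.245 = 3.1. The Matched Sham Set with 20 sham gives 8.8 × 0.265 = 2.3. The written version is now too wide even with 20 sham.

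**5. Planned effect.** Without trimming, SD = sqrt(8.8² + d² × n1 × n0/(n1 + n0)²) × sqrt(1/n1 + 1/n0):

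- as written, d = 4.5, 50/25: 2.22
- Matched Sham Set, d = 24, 50/20: 3.69

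With trimming (200 trials, 1,000 permutations each, 20 sham), across the three survival assumptions:

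- as written: SD 2.4 to 3.0, two-sided 5% cut-off 4.7 to 5.9 points
- Matched Sham Set: SD 4.4 to 5.4, cut-off 8.6 to 10.3 points

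The written SD is 44% to 46% smaller; at 70% sham survival, 2.62/4.75 = 0.55. With 37 sham, the SDs are 2.4 to 3.0 against 4.2 to 5.1. The observed statistic averages 27 to 28 points, and the largest p-value in any simulated trial was 0.001 under either procedure.

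**6. Floor of the p-value.** Counting the observed arrangement, the smallest value with 10,000 draws is 1/10,001, about 0.0001. The written rule gives 0 when no draw exceeds the observed value.

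**The case against.** **It may be a carried-over example.** Section 6.1 is general methodology. The 75, 50 and 25 first appear in the case labelled hypothetical, and the rank-based joint rank method in the same section is also illustrated with the 75 trial participants although Table 4 applies it to the Matched Sham Set. This is plausible. But the p-value steps are written as the method, with a fixed seed and number of draws, and nothing says the example is continuing. Section 6.3.1 repeats the ITT population. Even on the charitable reading, no procedure exists for the Matched Sham Set.

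**A reader might infer that the written distribution is far too narrow and the test always anti-conservative.** The SAP does not support that. The large gap in step 5 arises because a true 24-point difference inflates the Matched Sham Set's permutation variance; it does not measure type I error. Under the null the direction changes with the number matched and with the 12 mg outcome.

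**A reader might also infer that p will be printed as 0.** The raw proportion can be 0, but the SAP section gives no display format, and a zero would arise with the correct set too. Adding one moves p only from 0 to about 0.0001.

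**No conclusion turns on it.** This stands. The trimmed mean is supplementary, is absent from the sequential testing in Table 2, and gives p of at most 0.001 either way at the planned effect.

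**Conclusion.** The point holds as a mismatch between a written rule and its only planned use. Sections 6.1 and 6.3.1 work on the trial's ITT participants; Table 4 places the analysis in the Matched Sham Set. As written, the p-value is not a valid test of 50/28 mg versus sham.

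With all groups equal, the type I error at nominal 5% runs from about 8% (20 sham) through near nominal (30) to about 3% (37), and it also moves with the 12 mg outcome. At the planned effect with 20 sham the reference SD is about 45% too small, without changing the conclusion. These figures assume normal changes with SD 8.8 in every group and, for the planned effect, sham survival of 60% to 75%.

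It should be corrected, but severity is limited because the analysis is supplementary and outside the hierarchy.

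**What to change.** 1. Section 6.1, step 1: permute the treatment labels among all participants in the Matched Sham Set, keeping the observed numbers of 50/28 mg and sham subjects.
2. Section 6.3.1: change the trimmed-mean population from the ITT Set to the Matched Sham Set, to agree with Table 4. Without this the contradiction remains.
3. Compute p = (1 + number of draws with |T| ≥ |T0|)/(10,000 + 1).
4. State that permuting labels against an external, non-randomised control assumes exchangeability after matching.
5. Reconcile the 58/28 mg label with the 50/28 mg used elsewhere.

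Keep the 75-participant, 50/25 version only if a trimmed mean is added for the 12 mg comparison (Table 9). The cost is SAP wording and a few lines of code; no new data are needed.

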## **Responder Analyses of CHOP INTEND and HINE Section 2**

Product: Nusinersen	Statistical Analysis Plan
Study: 232SM203	Version: 3.0 Final

For CHOP INTEND it is planned to use multiple imputation to deal with missing data and the analysis will be performed using logistic regression. Should the number of responders be less than 5 in either group, Fisher's exact test will be used instead. In this scenario, it will not be possible to use multiple imputation and the following approach will be implemented to impute a missing response:

For a given timepoint such as Day 183, subjects who die or withdraw from the study prior to Day 183 will be counted as non-responders and will be included in the denominator for the calculation of the proportion of responders. In determining the response at Day 183 where a subject has missing response but the two immediate flanking visits both have an evaluable response an imputation will be performed. For example, the visit of interest is Day 183 and the immediate flanking visits are Day 135 and Day 279. If at both Day 135 and Day 279 the subject is a responder, then an imputation will be performed to count the missing Day 183 as a responder. For any other combination of missing/non response observed in flanking visits the subject will be considered a non-responder.

For HINE Section 2 motor milestone responders it is not planned to use multiple imputation. Therefore, if the endpoint is at Day 302 and the participants has a missing HINE Section 2 response, they will be considered to be a non-responder. In a situation where the endpoint is at Day 183 and flanking visits may be available the imputation approach described above for CHOP INTEND response will be implemented.

[figure not shown]

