## 2.2. Study Design

This 3-part study will evaluate the efficacy and safety of a high dosing regimen of nusinersen in approximately 145 participants. The study will be conducted at approximately 65 sites globally. Following the completion of this study, all eligible participants may elect to enrol in a separate long-term extension study (232SM302), pending study approval by ethics committees and the appropriate regulatory authorities. In regard to participants rolling over from Part B, this will be done without unblinding the participant's treatment group.

Part B will consist of a pivotal, double-blind, active-controlled treatment period with either 2 or 4 loading doses of nusinersen (for the 50/28 mg Group and Control Group, respectively) administered intrathecally followed by maintenance doses approximately every 4 months thereafter. Approximately 75 participants with infantile-onset SMA will be randomized in a 1:2 ratio to receive either the currently approved dosing regimen or a 50/28 mg dosing regimen.

In the Control Group, up to a total of 25 participants will receive 4 loading doses of 12 mg of nusinersen administered intrathecally (Days 1, 15, 29, and 64), followed by maintenance doses of 12 mg on Days 183 and 279 (and a sham procedure on Day 135).

Product: Nusinersen	Statistical Analysis Plan
Study: 232SM203	Version: 3.0 Final

In the 50/28 mg Group, up to a total of 50 participants will receive 2 loading doses of 50 mg of nusinersen administered intrathecally (Days 1 and 15) and 2 sham procedures on Days 29 and 64, followed by maintenance doses of 28 mg on Days 135 and 279 (and a sham procedure on Day 183). In order to maintain blinding sham procedures will be used as shown in the table below.

Arm	Dose 1	Dose 2	Dose 3	Dose 4	Dose 5	Dose 6	Dose 7
50/28 mg	D1	D15	D29	D64	D135	D183	D279
Group	(50 mg)	(50 mg)	(sham)	(sham)	(28 mg)	(sham)	(28 mg)
Control (12/12	D1	D15	D29	D64	D135	D183	D279
mg) Group	(12 mg)	(12 mg)	(12 mg)	(12 mg)	(sham)	(12 mg)	(12 mg)

Participants will remain at the clinic for at least 24 hours after each study treatment administration or sham procedure.

Randomization in Part B will be performed using interactive response technology (IRT) and the randomization will be stratified by disease duration as follows:

- $\leq$  12 weeks and
- > 12 weeks (time from age at symptom onset to age at informed consent)

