## 2.3. Sample Size Considerations

The justification for the sample size for the infantile-onset SMA population in Part B is detailed as follows.

For the purposes of sample size determination, it is assumed that the higher dose will achieve an additional 4.5 improvement in CHOP INTEND and additional 3% in survival over the 12 mg dose. For the infantile-onset SMA population in Part B, a sample size of approximately 50 participants in the 50/28 mg Group and 20 sham subjects from study CS3B will provide at least approximately 99% power for the primary endpoint to detect an improvement of 24 points

Product: Nusinersen	Statistical Analysis Plan
Study: 232SM203	Version: 3.0 Final

on CHOP INTEND and 23% survival rate benefit (compared to that observed in Study CS3B participants receiving sham control) at Day 183 based on the joint rank test at a 2 sided significance level of 0.05. This power calculation is based on simulations using data generated from a joint model of survival and functional change. The model used a difference of 24 points for the Day 183 change from baseline in CHOP INTEND total score (50/28 mg Group – Study CS3B Sham Control Group) and a population standard deviation of 8.8 for change from baseline.

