For each of the 100 imputed datasets, the endpoint will be compared between treatment groups using an ANCOVA model for continuous endpoints and logistic regression for binary endpoints as described in the main analysis for each endpoint. Additional detail such as how the joint rank test will be implemented and the adjustment for baseline covariates is described below and for each endpoint in Section 6.3 and 6.4

The estimates from the 100 fitted models will be combined to provide an overall estimate with corresponding confidence intervals and p-value using PROC MIANALYZE [Little et al, 2002].

For the continuous endpoints, the difference between treatments and the corresponding CI will be presented. For the analyses using logistic regression the odds ratio and corresponding CI will

Product: Nusinersen	Statistical Analysis Plan
Study: 232SM203	Version: 3.0 Final

be presented. In addition, the estimates of the binomial proportions in each treatment arm and the differences between treatments will be presented (Ratitch, 2013).

In the presentation of results from multiple imputed data, the number of subjects with missing data will be summarized.

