### Main Analysis

 The difference in the proportion of responders between treatment groups at Day 183 will be compared using logistic regression with the total number of motor milestones at baseline, baseline CHOP INTEND and disease duration at screening as covariates. Should the number of responders be less than 5 in either group, Fisher's exact test will be used instead. If Fisher's exact test is used, the unconditional confidence interval for the difference in response rates will be provided [Chan and Zhang 1999].

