### 6.5.2. Comparison: 50/28mg versus 12 mg Group from 232SM203

For the comparison of higher dose and 12 mg Group from 232SM203, some of the secondary endpoints will be repeated as listed below, also the proportion of CHOP INTEND responders at Day 183 and Day 302 and proportion of Motor Milestones responders at Day 302 will be analyzed.

Endpoint Ar	alysis Method	Analysis Population: further notes
Change in CHOP INTEND from baseline to Day 18.	3 Joint rank using multiple imputation (MI)	ITT set Repeat for Day 29 and 64.
Change in Motor Milestones total score from baselin to Day 183	e Joint rank using multiple imputation (MI)	ITT set
The Proportion of CHOP INTEND Responders at Da 183	ay Logistic regression or Fisher's Exact Test	ITT set

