patient's history, psychosocial circumstances, symptoms, behavior, and the impact of the symptoms on the patient's ability to function. The CGIC is administered by an experienced clinician who is familiar with the disease under study and the likely progression of treatment. The clinician makes a judgment about the total picture of the patient at each visit: the severity of the illness, the patient's level of distress and other aspects of impairment, and the impact of the illness on functioning. The CGIC is rated without regard to the clinician's belief that any clinical changes are or are not due to medication and without consideration of the etiology of the symptoms.

The CGIC is a 7-point scale that requires the clinician to assess how much the patient's illness has changed relative to a baseline state at the beginning of the intervention and is rated as follows: 1, very much improved; 2, much improved; 3, minimally improved; 4, no change; 5, minimally worse; 6, much worse; or 7, very much worse.

CGIC should be assessed consistently by the same rater for each study participant. A separate CGIC assessment will be performed by the Investigator (Principal Investigator or Sub investigator) and caregiver.

Clinical Global Impression of Change (CGIC) for the physician and caregiver at Day 302 will be analyzed as an ordered categorical score and as a dichotomized response: "much improved" or "very much improved" versus other responses.

The proportion of subjects with each CGIC score and with the dichotomized response of either "much improved" or "very much improved" will be summarized by visit and treatment group.

The difference in CGIC dichotomized response rate between 50/28 mg Group and Control Group will be analyzed using a logistic regression model with terms for treatment group and disease duration. Participants who die or withdraw from the study, prior Day 302, will be counted as 'non responders'.

The odds ratio, its 95% CI and the p-value for 50/28 mg Group compared to the Control Group will be presented. The proportion of CGIC responders at other visits will also be analyzed in a similar way. In a situation where the model does not converge then exact logistic regression (Hirji, K. F. 2005) will be performed.

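### Part B infantile-onset SAP: the rule for leaving logistic regression counts responders only, so an arm with no non-responders stays in a separated model with an uninformative pooled p-value

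*SAP*

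**What the plan says.** All references are to the Part B infantile-onset SAP unless stated.

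- Section 6.1, on CHOP INTEND and HINE Section 2 responders, plans logistic regression (with multiple imputation for CHOP INTEND) and then states: "Should the number of responders be less than 5 in either group, Fisher's exact test will be used instead". Section 6.4.1 repeats this trigger for HINE Section 2 responders at Day 183, the second test in the hierarchy, where groups are "compared using logistic regression with the total number of motor milestones at baseline, baseline CHOP INTEND and disease duration at screening as covariates". Neither place mentions non-responders, separation or convergence.
- Section 6.1, on multiple imputation: "The estimates from the 100 fitted models will be combined to provide an overall estimate with corresponding confidence intervals and p-value using PROC MIANALYZE".
- Section 6.5.1 defines a CHOP INTEND responder as a gain of at least 4 points and counts deaths and withdrawals as non-responders. It also allows Fisher's test when low counts make logistic regression impossible, without saying which count or what makes a fit impossible. That section covers the sham comparison.
- Section 6.5.2 applies the responder analysis between two active arms: "the proportion of CHOP INTEND responders at Day 183 and Day 302". Table 17 gives the method only as logistic regression or Fisher's exact test.
- Section 2.2 sets the arm sizes: "up to a total of 50 participants will receive 2 loading doses of 50 mg" and "up to a total of 25 participants will receive 4 loading doses of 12 mg".
- Section 2.3: "The model used a difference of 24 points for the Day 183 change from baseline in CHOP INTEND total score". It also assumes a further 4.5 points over 12 mg and an SD of 8.8.

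**The concern.** Maximum-likelihood logistic regression fails when either outcome cell of an arm is empty, but the rule guards only the responder cell. A 4-point threshold is low against an assumed 24-point advantage over sham, so an active arm in which every infant responds is conceivable. The treatment coefficient then has no finite estimate, the software stops at an arbitrary large value with a very large standard error, and the Wald p-value approaches 1 however different the arms are. Pooling makes this worse, because a minority of separated imputed datasets is enough to swamp the combined standard error. A real difference between 50/28 mg and 12 mg in response rate could be reported as no difference, and any substitute method would then be chosen after the data were seen.

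**Working it through.** **The plan's own figure.** The only power stated is at least about 99% for the primary endpoint, 50 versus 20. A normal approximation gives SE = 8.8 × √(1/50 + 1/20) = 2.33 and 24/2.33 = 10.3, so power is essentially 1. This agrees with the SAP, which used a joint-rank simulation, and is not in dispute. No figure is stated for the responder analyses.

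**What the rule does, table by table** (50 versus 25 infants, unadjusted; both responder counts are 5 or more, so Fisher's test is never triggered):

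| Responders | log OR (SE) | Wald p | Likelihood-ratio p | Firth p | Fisher p |
|---|---|---|---|---|---|
| 50/50 v 20/25 | 18.8 (3448) | 0.996 | 0.0006 | 0.0019 | 0.0031 |
| 50/50 v 22/25 | 18.2 (3448) | 0.996 | 0.009 | 0.022 | 0.034 |
| 49/50 v 20/25 | 2.51 (1.13) | 0.026 | 0.008 | 0.011 | 0.014 |
| 48/50 v 20/25 | 1.79 (0.88) | 0.041 | 0.030 | 0.032 | 0.037 |

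The Wald value in the first two rows depends on where iteration stops (0.58 after 8 iterations for the first row) but is not significant at either stopping point. With two simulated covariates added, every 50/50 dataset separated. At 49/50 v 20/25 none did, and the median Wald p was 0.027.

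**Pooling.** Suppose one 50/28 mg infant is imputed as a responder in 10 of 100 datasets (50/50) and as a non-responder in 90 (49/50), against 20/25.

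- Pooled log OR = 0.1 × 18.82 + 0.9 × 2.51 = 4.14.
- Within-imputation variance = 0.1 × 3447.6² + 0.9 × 1.13² ≈ 1,188,600, so SE ≈ 1090. The between-imputation variance is negligible beside this.
- z = 4.14/1090 = 0.004, p = 0.997.

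**How likely is an empty non-responder cell?** The SAP gives no sham mean change and no response rates, so a sham mean m of -8 to 0 is assumed. Day 183 response is P(N(m + 24, 8.8) ≥ 4) for 50/28 mg and P(N(m + 19.5, 8.8) ≥ 4) for 12 mg (19.5 = 24 - 4.5), each multiplied by (1 - loss), with losses counted as non-response. With arm response rates p₁ and p₀, the chance that at least one arm has no non-responder is 1 - (1 - p₁⁵⁰)(1 - p₀²⁵).

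| Assumed sham mean | Response without loss, 50/28 mg; 12 mg | No loss | 5% loss | 10% loss | 8% and 20% loss |
|---|---|---|---|---|---|
| -8 | 0.914; 0.803 | 2% | 0.2% | <0.1% | <0.1% |
| -4 | 0.966; 0.904 | 24% | 4% | 0.7% | 0.3% |
| 0 | 0.989; 0.961 | 72% | 14% | 3% | 1% |

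The last column uses the hypothetical losses in the SAP's trimmed-mean example (4 of 50 and 5 of 25). In the 72% corner, 0.560 + 0.369 - 0.207 = 0.722; the 0.207 is both arms empty, where there is no difference to miss.

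**Cost in power, written rule versus Fisher** (assumed true rates, 50 v 25): 99% v 80%, 0.23 v 0.83; 98% v 80%, 0.35 v 0.74; 95% v 75%, 0.59 v 0.64; 90% v 70%, 0.55 v 0.51. The loss follows the chance of no non-responder among 50: 0.605 at 99%, 0.364 at 98%, 0.077 at 95%, 0.005 at 90%.

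**The case against.** The strongest reply is that the failure is rare and peripheral. Much of this stands.

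- **Near-universal response is not enough.** A reader might infer that the model breaks whenever almost all infants respond, or cite the chance of fewer than 5 non-responders in an arm (17% to nearly 100% under the same assumptions with 0 to 10% loss). That is the wrong event: one non-responder in the top arm restores a usable Wald test.
- **Losses fill the cell.** Deaths and withdrawals count as non-responses, and in infantile-onset SMA some are to be expected. The 72% needs no loss at all and a sham mean of 0. The convention is stated in Section 6.5.1 and in the Fisher rule of Section 6.1; its use in the 12 mg comparison is assumed here.
- **The main exposure is supplemental.** The 50/28 mg versus 12 mg responder analyses lie outside the hierarchy. The ranked functional comparisons of those arms use the joint-rank test and are unaffected, and arm proportions are reported alongside.
- **Section 6.5.1 may cover it.** The low-counts clause could be read that way, but it sits in the sham section, and a separated model usually still prints output, so impossibility is not clearly met.
- **The second-ranked test.** A reader might infer that replacing the adjusted model by Fisher's test when few sham infants respond is also a defect. The documents do not support that: the fallback is prespecified, has its own confidence interval, and follows matching on two of the three covariates; no changed conclusion has been shown. HINE Section 2 responders use no multiple imputation and the SAP does not name a Wald test. The separation problem arises there only if sham has 5 or more responders, the 50/28 mg arm has no non-responder and a Wald test is used.

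**Conclusion.** The gap is real but narrow. As written, the rule keeps a separated logistic model when an arm has no non-responders, in the observed data or in even a minority of imputed datasets, and the pooled p-value is then uninformative. The arithmetic on 50/50 versus 20/25 does not depend on any planning assumption. How often this would happen does: 2% to 72% with no losses, 14% or less at 5% loss, and about 1% or less at the SAP's illustrative losses, all for an assumed sham mean change of -8 to 0 and Day 183 normality. No Day 302 planning figures exist, so nothing is claimed about its likelihood there. The primary endpoint and the joint-rank tests are not touched. It is worth correcting because a stated rule can give a plainly wrong result and the repair is cheap. A figure in this part of Section 6.1 is not visible in the public copy; the conclusion rests on the text.

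**What to change.** In Sections 6.1 and 6.4.1, and for Tables 6, 16 and 17, add: *If either group has no non-responders, or if separation or non-convergence is detected in the observed data or in any imputed dataset, Firth penalised-likelihood logistic regression with the same covariates (and multiple imputation where planned) will be used for all datasets, with Fisher's exact test reported as support.* Using one estimator for all datasets keeps the pooling coherent.

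Do not simply extend the Fisher trigger to fewer than 5 non-responders. That would drop covariate adjustment and multiple imputation in cases such as 48/50 versus 20/25, where the logistic model still works.

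The cost is one sentence and one procedure option. The small downside is that the penalised odds ratio is slightly shrunk. The later-onset SAP already names fallbacks for logistic models that do not converge (Cochran-Mantel-Haenszel for HFMSE responders, exact logistic regression for CGIC), so planning for model failure is not new to this trial.
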